### **7.1.2. Aim 2:**

Analyses here will assess changes in craving and depression symptom scores as mediators of bupropion treatment effects at weeks 10 of treatment and 24 weeks post-TQD. These measures are continuous difference scores. Our sample of 360 is well above the minimum sample of 200 recommended for such analyses (169-170). The mediation hypotheses will examine the proportion of variance in treatment effect explained (171-172), and we will test each mediation hypothesis with a z-score generated using the delta method. Our sample of 360 gives us 80% power to observe small effects in a 1-sample test ( $\delta = 0.16$ ) when testing at  $\alpha = 0.05$ . There are 2 proposed mediating pathways (depression and craving) between treatment and outcome, so our type-1 error will be corrected to 0.025. A sample of 360 gives us 80% power to detect small-to-medium effects ( $\delta=0.35$  SD) for changes in the proposed mediators, which we have seen in previous trials (15, 52).

## **7.2. Statistical Analyses**

[name] will oversee analyses, which will be conducted using Stata, SAS, or R-Language software. Preliminary analyses will assess sample characteristics (e.g., dependence, race) by treatment using t-test or contingency table methods. These variables will also be examined for their relationship to completion of outcome assessments. Variables related to treatment arm or completion of follow ups will be included as covariates in analyses of study aims. Compliance measures will be evaluated across treatment arms, and controlled for in primary analyses. We will examine the correlation between self-report and pill count data and week-5 bupropion plasma levels. We will use intent-to-treat as the primary method to evaluate study aims.

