ii. Variation in *CYP2B6*. Two studies from [name] group have also shown that a variant (*CYP2B6\*6*) in the gene encoding the cytochrome P450 enzyme 2B6 (which metabolizes bupropion to its major active metabolite, hydroxybupropion) moderated bupropion response. First, in a study of 326 Caucasian smokers (75), at the end of treatment and at 6-month follow up, carriers of the variant allele (45% of the sample) had significantly higher quit rates than placebo-treated subjects (32.5% vs. 14.3 and 31.2% vs. 12.9%, respectively). In the group with no variant alleles, bupropion treatment was no better than placebo in promoting abstinence. Second, in a 7-week treatment trial in 540 African-American light smokers (<11 CPD), 42.9% of bupropion-treated subjects were not adherent to treatment (20). In the 154 treatment-adherent bupropion subjects, higher hydroxybupropion (but not bupropion) concentrations resulted in higher rates of smoking cessation after 3, 7, and 26 weeks of treatment (ORs = 2.82, 2.96, and 2.37, respectively). Using alleles that have been shown to encode a reduced-function enzyme, [name] and colleagues found that the slow metabolizer group had significantly lower hydroxybupropion concentrations and both the slow metabolizer and intermediate groups had lower hydroxybupropion/bupropion ratios than faster metabolizers. Because 16% of African Americans and 6% of Caucasians are slow metabolizers, with the proportion of intermediate metabolizers in these groups being 48% and 38%, respectively, the potential for variation in *CYP2B6* to moderate treatment response is substantial. However, because of other influences on bupropion and hydroxybupropion concentrations (e.g., concomitant medications, hormone status, and bupropion adherence), there are inconsistent findings on the impact of *CYP2B6* variation on smoking cessation. In the present study, we will measure *CYP2B6* genotype, bupropion and hydroxybupropion concentrations, medication adherence, and enzymatic activity and the impact of these on the likelihood of smoking cessation (and risk of AEs).

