### **7.2.1. Missing Data:**

We will examine whether the rate of missing data, primarily our smoking cessation outcome data, is related to a range of potential variables, including treatment arm allocation, and demographic and smoking-related variables. Standard bivariate statistical methods will be used to identify correlates of missing data. Variables associated with the rate of missing data ( $p < 0.05$ ) will be included as covariates in the analyses of aims. Items missing at random from assessments will be imputed prior to calculating final scores using conditional means, estimated with an iterated version of Buck's method (173). We will aim to avoid dropout and missed sessions by keeping participants connected to the trial and motivated to complete measures. In our clinical trials, close monitoring of participants and the use of incentives to offset travel costs have resulted in adherence and retention rates >80% (52). Primary analyses will assume that all participants for whom smoking outcome data are unavailable are smokers (intent-to-treat), which is conventional in smoking cessation research. Because this assumption can attenuate the differences between study groups in quit rates, we will also conduct a "completers-only" analysis, as done previously (174).

CONFIDENTIAL

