**H2:** We will compare treatment arms for equivalence of the frequency of moderate-to-severe AEs (individual and total). The hypothesis test for equivalence is a test of whether the OR is out of the prescribed range for the difference between the treatment arms. Using logistic regression, we will conduct two one-sided tests against predefined upper and lower equivalence boundaries on percent reporting only mild AEs. The test-statistic will be the z-score corresponding to the log of the OR. This provides a more valid test of the potential safety of bupropion for pregnant smokers than a simple comparison of mean responses on a measure of AEs.

**H3:** Mean birth weight will be compared for treatment groups using a two-sample t-test, in the context of multiple linear regression. The regression format allows us to add covariates to adjust for imbalances in participant characteristics between treatment arms. Treatment will be entered as a binary indicator. In a secondary analysis, we will also compare the percentage of participants in each group that delivers an infant of LBW (1500-2500 g) or preterm delivery. These secondary hypotheses will be tested using the z-score corresponding to the OR that will be estimated using logistic regression.

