### **7.3. Participant Population for Analysis**

Data from protocol-compliant participants will be used for analysis.

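### The H2 equivalence test has no settled analysis population, and both populations the plan names can lean toward declaring bupropion equivalent on adverse events

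*Combined protocol and SAP*

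**What the plan says.** Section 7.2 (Statistical Analyses) sets the general rule: "We will use intent-to-treat as the primary method to evaluate study aims". The Study Summary repeats it. The same paragraph of 7.2 adds: "Compliance measures will be evaluated across treatment arms, and controlled for in primary analyses". Section 7.3, the only section devoted to the analysis population, reads in full: "Data from protocol-compliant participants will be used for analysis".

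H2 belongs to Aim 1. Section 7.2.2 describes its test: "Using logistic regression, we will conduct two one-sided tests against predefined upper and lower equivalence boundaries on percent reporting only mild AEs". It gives no population for that test. Section 7.1.1 explains that equivalence testing was chosen because a non-significant difference cannot show that the drug is safe.

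The one sensitivity analysis named, completers-only in section 7.2.1, is justified by its effect on quit rates and not by AEs. Section 7.2.4 will explore whether AE risk is moderated by plasma bupropion and hydroxybupropion levels. That analysis is exploratory and is not an equivalence test.

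On adherence, section 7.2.1 reports rates above 80% in the team's earlier trials. Section 1.1 cites an external 7-week trial in light smokers in which "42.9% of bupropion-treated subjects were not adherent to treatment". It also reports poor, limited or very low adherence in the nicotine-replacement trials in pregnancy.

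**The concern.** Non-adherence works in opposite directions for H1 and H2. For H1, a superiority test, women who do not take bupropion make a positive result harder to reach. For H2 they have AE rates closer to placebo, shrink the observed difference and make equivalence easier to reach. A compliance main effect in the model does not undo this, because the treatment coefficient still averages over takers and non-takers.

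The section 7.3 set does not solve the problem. Section 3.2 says AEs can lead to dose reduction or suspension, and section 10.1 has women with Code 3 or Code 4 events told to stop the study drug pending medical consultation. Compliance can therefore be a consequence of an AE. A compliant set, which the plan does not define, can exclude the very women whose AEs the test is meant to count.

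The plan says of the equivalence test: "This provides a more valid test of the potential safety of bupropion for pregnant smokers". If the claim becomes easier to reach as fewer women take the drug, or as more of them stop because of AEs, the error falls on the unsafe side in pregnant women and their offspring.

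**Working it through.** **The plan's own H2 figures.** Section 7.1.1 states 82% power (45% v 47% free of moderate-to-severe AEs, window 0.30–0.60) and 81% (30% v 30%, ±15%). Section 7.1 sets two one-sided tests at 0.025 each, and section 5.3 gives 180 per arm. With the formula below I get about 63% for the first (limits −17 and +13 points around 47%) and 75% for the second. Neither stated figure reproduces. A single one-sided test at 0.025 with 15 points to the limit gives 81.5% for the first. This is a separate matter; the error rates below do not depend on the stated powers.

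**Formula.** With pC the AE-free proportion on placebo, pT that on bupropion under intent-to-treat, and d = pT − pC:

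SE = √[(pT(1−pT) + pC(1−pC)) / 180]

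P(equivalence) = Φ((0.15 − d)/SE − 1.96) + Φ((d + 0.15)/SE − 1.96) − 1

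**Dilution model (assumption).** Let e be the excess in women who take bupropion, q the non-adherent fraction, and h the fraction of non-adherent women who carry the takers' AE risk because they were exposed before stopping. Then d = −e × (1 − q + h·q). I use h = 0 (non-adherent women have the placebo rate) and h = 0.5.

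**Inputs.** pC = 0.47 and margin ±0.15 (section 7.1.1; 0.30–0.60 is ±15 points around 45%). q = 0; 0.20, the bound implied by adherence above 80% (section 7.2.1); and 0.429 (section 1.1).

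**One case in full.** For e = 0.15, q = 0.20 and h = 0: d = −0.12, pT = 0.35, and SE = √[(0.2275 + 0.2491)/180] = 0.0515. The harm-side term is Φ(0.03/0.0515 − 1.96) = 0.084. The other term is 0.9995. The result is 8.4%.

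| Excess in takers | Non-adherence | d and P(equivalence), h = 0 | d and P(equivalence), h = 0.5 |
|---|---|---|---|
| 15 points | 0% | −15.0; 2.5% | −15.0; 2.5% |
| 15 points | 20% | −12.0; 8.4% | −13.5; 4.8% |
| 15 points | 42.9% | −8.6; 23.0% | −11.8; 9.0% |
| 20 points | 0% | −20.0; 0.2% | −20.0; 0.2% |
| 20 points | 20% | −16.0; 1.5% | −18.0; 0.5% |
| 20 points | 42.9% | −11.4; 10.2% | −15.7; 1.8% |

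**Robustness, h = 0, excess of 15 points.** On the log-odds-ratio scale, with limits from 0.30 and 0.60 against 0.45, the figures are about 3%, 10% and 28% at 0%, 20% and 42.9% non-adherence. With a 30% placebo AE rate and ±15 points they are 2.5%, 8.6% and 25%.

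**What the margin then means.** With h = 0, an intent-to-treat difference exactly at 15 points corresponds to an excess in takers of 0.15/0.80 = 18.8 points at 20% non-adherence and 0.15/0.571 = 26.3 points at 42.9%.

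**The section 7.3 set.** The documents give no definition of compliance and no rate of stopping for AEs, so its bias cannot be sized. Only its possible direction follows from sections 3.2 and 10.1.

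**The case against.** The strongest reply is that the plan does not anticipate heavy non-adherence. A reader might infer from section 1.1 that it does, but the documents do not support that. The 42.9% comes from another trial and is cited in a discussion of CYP2B6, and the poor adherence in pregnancy was to nicotine replacement. The plan points to rates above 80% and adds daily text messages, an optional free phone and payment for returned blister packs. This stands: 20% is the figure to lead with, and 42.9% is a stress case.

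Second, being non-adherent is not the same as being unexposed. AEs are checked at weeks 1, 3, 5, 7 and 10, and intent-to-treat already counts the AE of a woman who takes the drug, has the event and stops. This also stands, and it is why the h = 0.5 column is given. In that column a 20-point excess passes in under 2% of trials.

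Third, a reader might conclude that H2 is settled as intent-to-treat and that no exposure-based look at AEs is planned. Neither is right. Section 7.3 contradicts section 7.2, and section 7.2.4 plans an exploratory analysis of AE risk by plasma level. What remains is that no exposure-based analysis bears on the equivalence claim itself.

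Fourth, restricting H2 to adherent women would be costly as well as selective. At 45% v 47% and ±15 points, the formula above with 103 per arm (0.571 × 180) gives about 15% power, against about 60% with 180. That argues against an adherent-only subset, but not against an analysis of all women who took a dose.

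**Conclusion.** The point holds as a conflict over the H2 population combined with a moderate loss of protection against false equivalence. At the adherence the team reports for its own trials, a true excess at the 15-point margin in takers would be declared equivalent in up to about 5–8% of trials, against the nominal 2.5%. At the external trial's 42.9% it would be 9–23%. These figures assume 180 per arm, 47% AE-free on placebo, ±15 points, 0.025 per side, and adherence unrelated to underlying AE risk. The ends of each range differ only in whether half or none of the non-adherent women carried the drug's AE risk before stopping.

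The 23% should not be read as the error rate to expect. It needs both an adherence level that the plan does not project and no drug AEs among non-adherent women. Nor is replacing intent-to-treat by the compliant set the answer, since that set can lean the same way.

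**What to change.** - **Reconcile sections 7.2 and 7.3 for H2.** Keep intent-to-treat, and state that the section 7.3 compliant set is not used for H2.
- **Prespecify an on-treatment analysis beside it in section 7.2.2.** Include all women who took at least one dose. Count any moderate-to-severe AE from the first dose to the last dose plus a fixed carry-over period, set before unblinding and identical in both arms. A woman who stops because of an AE then keeps that AE. Use the same proportion or odds-ratio scale and the same margin as the main test.
- **Report the adherence achieved**, by pill count and week-5 plasma level, and the time on treatment by arm. Unequal time on treatment would affect how the on-treatment proportions compare.
- **Tie the wording to both analyses.** Claim safety equivalence only if the harm-side limit holds in each. Otherwise report no difference at the adherence achieved.
- **Do not use two alternatives as decision criteria.** AEs per week on drug have no margin in the plan. Dividing the intent-to-treat difference by the proportion with drug at week 5 is biased when women stop early because of AEs.

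The cost is SAP wording and one extra analysis of data already collected: AE checklists, returned blister packs and week-5 plasma levels. The price is that equivalence becomes harder to claim when adherence is poor. Power under the joint rule can be no higher than for intent-to-treat alone; the loss cannot be sized, because the documents do not project how many women will take no dose or stop early.

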### **7.2.1. Missing Data:**

We will examine whether the rate of missing data, primarily our smoking cessation outcome data, is related to a range of potential variables, including treatment arm allocation, and demographic and smoking-related variables. Standard bivariate statistical methods will be used to identify correlates of missing data. Variables associated with the rate of missing data ( $p < 0.05$ ) will be included as covariates in the analyses of aims. Items missing at random from assessments will be imputed prior to calculating final scores using conditional means, estimated with an iterated version of Buck's method (173). We will aim to avoid dropout and missed sessions by keeping participants connected to the trial and motivated to complete measures. In our clinical trials, close monitoring of participants and the use of incentives to offset travel costs have resulted in adherence and retention rates >80% (52). Primary analyses will assume that all participants for whom smoking outcome data are unavailable are smokers (intent-to-treat), which is conventional in smoking cessation research. Because this assumption can attenuate the differences between study groups in quit rates, we will also conduct a "completers-only" analysis, as done previously (174).

CONFIDENTIAL

### **7.2.2. Specific Aim 1: To compare the efficacy of bupropion with placebo for smoking cessation in pregnant smokers.**

For **H1**, we will test for treatment group differences in a binary abstinence outcome that is a repeated measure using a generalized estimating equations (GEE) model with a logit link. Quit rates at the end of week 10 of treatment and 24 weeks post-TQD will represent our primary outcome variables. Medication group (bupropion vs. placebo) and time point (end of week 10 of treatment and 24 weeks post-TQD) will be treated as categorical predictor variables, and the model will predict separate effects of treatment on abstinence at each time point (an interaction). Our initial analyses will be stratified by site, and we will carefully examine the models for differences by site, testing for an overall interaction. We will use baseline depression (PHQ-9 score of 10) to stratify the randomization. The model may include a small number of covariates added to control error or adjust for confounding [e.g., age, history of pre-term delivery, baseline gestational age, daily smoking rate]. Any variables found to be associated with both outcome and treatment assignment will be entered as covariates. In the absence of an overall interaction (by site), we will pool the study population and account for site in the model as a binary predictor. To evaluate the effectiveness of randomization, we will compare summary statistics for participant characteristics in the two study arms. If there is an imbalance in participant characteristics, statistical adjustment will be used to ensure that the initial results were not biased by it.

Because many participants will fail to become completely abstinent, but may show a reduction in smoking, we will examine cigarette consumption as a secondary outcome. The analysis will be similar to the primary analysis, except that we examine the effect of treatment arm on daily cigarette counts using a GEE model with a negative-binomial link. Likewise, time to (recurrent) event models will be fitted using Cox regression, stratified by event sequence, as in Schnoll et al. (52), to assess lapse and recovery events over 24 weeks.

**H2:** We will compare treatment arms for equivalence of the frequency of moderate-to-severe AEs (individual and total). The hypothesis test for equivalence is a test of whether the OR is out of the prescribed range for the difference between the treatment arms. Using logistic regression, we will conduct two one-sided tests against predefined upper and lower equivalence boundaries on percent reporting only mild AEs. The test-statistic will be the z-score corresponding to the log of the OR. This provides a more valid test of the potential safety of bupropion for pregnant smokers than a simple comparison of mean responses on a measure of AEs.

**H3:** Mean birth weight will be compared for treatment groups using a two-sample t-test, in the context of multiple linear regression. The regression format allows us to add covariates to adjust for imbalances in participant characteristics between treatment arms. Treatment will be entered as a binary indicator. In a secondary analysis, we will also compare the percentage of participants in each group that delivers an infant of LBW (1500-2500 g) or preterm delivery. These secondary hypotheses will be tested using the z-score corresponding to the OR that will be estimated using logistic regression.

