Statistical Methodology	
Preliminary analyses will assess sample characteristics (e.g., age, race, study site) by treatment using t-test or contingency table methods. These variables will also be examined for their relationship to completion of outcome assessments. Variables related to treatment arm or completion of follow ups will be included as covariates in analyses of study aims. Compliance measures will be evaluated across treatment arms, and controlled for in primary analyses. We will use intent-to-treat as the primary method to evaluate study aims. For Aim 1, we will test treatment group differences in a binary abstinence outcome that is a repeated measure using a generalized estimating equations (GEE) model with a logit link. Quit rates after 10 weeks of study medication and at 24 weeks post-TQD will represent our primary outcome variables. Medication group (bupropion vs. placebo) and time point (10 and 24 weeks) will be treated as categorical predictor variables, and the model will predict separate effects of treatment on abstinence at each time point (an interaction). Mean birth weight will be compared for treatment groups using a two-sample t-test, in the context of multiple linear regression. We will also compare treatment arms for equivalence of the frequency of moderate-to-severe adverse events (individual and total). For Aim 2, we will use a regression-based path model approach to examine mediation of treatment effects by changes in depression and craving scores, which will be entered in the model as standardized pre-post differences, continuously distributed and treated as normal in linear regression. The effects of treatment arm on mediators, and of mediators on outcome, will be assessed using linear regression and standardized variables. For Aim 3, we will explore whether the risk of adverse events and the efficacy of bupropion treatment (vs. placebo) is moderated by: 1) the rate of nicotine metabolism and variation in CYP2A6; 2) the rate of bupropion metabolism (i.e., variation in CYP2B6 and plasma concentrations of bupropion and hydroxybupropion); and 3) variation in social/behavioral variables, including weight concerns, body image, and the presence of other smokers in the home.

CONFIDENTIAL

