## **2. Study Objectives**

**Specific Aim 1:** Conduct a 10-week placebo-controlled trial of bupropion 300 mg/day in 360 pregnant smokers who are at 13–26 weeks gestation. We will monitor smoking behavior and adverse effects (AEs) of the medication during a 10-week treatment period, with follow up for

CONFIDENTIAL

the remainder of the pregnancy (measuring length of gestation, rate of pregnancy complications, and birth outcomes). We will also provide two booster counseling sessions at weeks 2 and 6 postpartum and a final research evaluation at 24 weeks post-TQD. We will use text messages to send pregnancy-relevant information and medication-adherence cues based on their demonstrated ability to improve adherence in various populations (e.g., 22, 23). We hypothesize that:

**H1:** Bupropion-treated women will have a greater rate of biochemically confirmed cigarette abstinence than placebo-treated women.

**H2:** There will be no significant differences between treatment arms in the frequency of severe treatment-related AEs.

**H3:** Bupropion treatment will result in a higher birth weight than placebo.

**Specific Aim 2:** Assess changes in depression symptoms and craving as mediators of bupropion's effect on quit rates.

**Exploratory Aim:** Explore genetic, metabolic, and social/behavioral moderators of the efficacy of bupropion on cigarette abstinence and safety. To generate new hypotheses, we will explore whether the risk of AEs and the efficacy of bupropion treatment (vs. placebo) is moderated by: 1) the rate of nicotine metabolism (i.e., nicotine metabolite ratio (NMR)) and variation in *CYP2A6*; 2) variation in *CYP2B6* and plasma concentrations of bupropion and hydroxybupropion; and 3) variation in social/behavioral variables, including weight concerns, body image, and the presence of other smokers in the home.

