## 7. Statistical Plan

### 7.1. Power

A power analysis is provided only for the primary aims because the exploratory aim is hypothesis generating. Most of our power calculations were approximated as 2-sided t- or z-tests, with  $\alpha = 0.05$ , using PASS Software (Power and Sample Size, NCSS Software, Kaysville, UT). Equivalence testing was approximated as two one-sided tests, with  $\alpha = 0.025$  each.

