#### 7.1.1. Aim 1:

The primary efficacy analysis (**H1**) is a comparison in week 10 (of treatment) and week 24 post-TQD of CO-confirmed 7-day point prevalence quit rates for the placebo and bupropion groups. For the week-10 comparison, we expect that the quit rates in the placebo and bupropion arms would approximate those reported in bupropion trials in the general population of smokers (i.e., placebo = 21.2%; bupropion = 35.9%, OR = 2.1; ref. 44). A sample of 360 provides 88% power to detect a significant between-group effect. The OR for bupropion treatment is similar at 24 weeks, based on Jorenby et al. (168) and our own data, and results from 10 and 24 weeks are highly correlated ( $\rho > 0.7$ ). Thus, we have 80% power to detect a significant difference between treatment arms.

Safety analyses (**H2**) will examine maternal safety across the 10-week treatment and 24-week follow-up periods and fetal and birth outcomes. Key maternal and fetal outcomes to be compared across treatment groups include rates of moderate-to-severe side AEs of bupropion (from the AE checklist). Key birth outcomes will include Apgar scores, birth weight, duration of pregnancy, rate of obstetrical complications, and need for NICU admission. These analyses will involve a test of equivalence because we cannot use standard statistical tests to conclude that a non-significant comparison shows that the drug is safe (i.e., "the absence of evidence is not evidence of its absence"). In our past study with bupropion, 45% of bupropion-treated participants reported no moderate-to-severe AEs, vs. 47% of participants on placebo, a 2% difference. With the present sample size, we will have 82% power to detect similar equivalence between treatment arms on the frequency of moderate-to-severe AEs over the course of the trial, given that AEs are not significantly different between treatment arms, using an equivalence window of 0.30 to 0.60. Likewise, Oncken et al. (47) reported 38% AEs for the placebo group

CONFIDENTIAL

and 25% in the nicotine group. An equivalence test with placebo and bupropion groups both at 30% and an equivalence window for bupropion of +/-15% provides 81% power.

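### Week 10 and week 24 abstinence are both primary for H1 with no rule for combining them, so two-sided familywise error can reach about 8.3% if either may be claimed

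*Combined protocol and SAP*

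**What the plan says.** The Study Summary and section 7.2.2 both name two primary abstinence outcomes. The summary has "Quit rates after 10 weeks of study medication and at 24 weeks post-TQD will represent our primary outcome variables"; section 7.2.2 has "Quit rates at the end of week 10 of treatment and 24 weeks post-TQD will represent our primary outcome variables". Both are analysed in one GEE model with treatment and time point as categorical predictors, and "the model will predict separate effects of treatment on abstinence at each time point (an interaction"). So there are two treatment contrasts, and the plan does not name one as decisive or call for a joint test.

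H1 in section 2 is directional and names no time point: "Bupropion-treated women will have a greater rate of biochemically confirmed cigarette abstinence than placebo-treated women".

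Section 7.2.2 gives no significance level for H1. The nearest statement is in section 7.1, where "Most of our power calculations were approximated as 2-sided t- or z-tests" at alpha 0.05. Section 7.1.1 bases the week-10 comparison on "placebo = 21.2%; bupropion = 35.9%, OR = 2.1; ref. 44" and states 88% power with 360 women. It then says that the odds ratio is similar at 24 weeks and that the two results correlate above 0.7, and concludes that power is 80%. It gives no week-24 rates and no alpha for that second figure.

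For Aim 2, with two mediating pathways, section 7.1.2 does make an adjustment: "so our type-1 error will be corrected to 0.025". Nothing comparable appears for H1.

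**The concern.** With two primary contrasts and no decision rule, the plan does not say what counts as success if one is significant and the other is not. A split result is foreseeable. Section 1.1 cites a UK nicotine-patch trial with quit rates of 21.3% against 11.7% at one month, but 9.4% against 7.6% for abstinence from the quit date to delivery.

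If either result may be reported as support for H1, two chances at 0.05 replace one, and the error rate for the main claim is no longer the nominal one. The gap stands out because the authors correct for two tests in Aim 2. A rule chosen after the data are seen cannot restore error control.

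**Working it through.** **Inputs.** Quit rates of 21.2% and 35.9% (7.1.1); 180 per arm (5.3); two-sided alpha 0.05 (7.1, stated for the power calculations); correlation ρ > 0.7 between week-10 and week-24 results (7.1.1). Missing outcomes count as smoking (7.2.1), so all 360 women enter the analysis.

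**Step 1: reproduce the 88%.**
- Difference: 0.359 − 0.212 = 0.147.
- Unpooled SE: √(0.212×0.788/180 + 0.359×0.641/180) = 0.0470.
- 0.147/0.0470 = 3.13.
- Power at two-sided 0.05: Φ(3.13 − 1.96) = 87.9%; with a pooled null variance, 87.3%.
- Power at two-sided 0.025: Φ(3.13 − 2.24) = 81.3%; pooled, 80.4%.

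The stated 88% fits the full 0.05 and not a split alpha.

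**Step 2: error if either time point suffices.** Under no effect, treat the two z statistics as bivariate normal with correlation ρ.
- Two-sided: P(|Z₁| > 1.96 or |Z₂| > 1.96).
- In bupropion's favour only: P(Z₁ > 1.96 or Z₂ > 1.96), nominal 2.5%.

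| ρ | Two-sided, at least one | In bupropion's favour |
|---|---|---|
| 0.7 | 8.3% | 4.2% |
| 0.8 | 7.8% | 3.9% |
| 0.9 | 7.0% | 3.5% |
| 0.95 | 6.5% | 3.2% |
| 1 | 5.0% | 2.5% |

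Because the protocol puts ρ above 0.7, the first row is the upper end of the range. A simulation of correlated binary outcomes (180 per arm, 21.2% quitting at both times, 200,000 runs) gave two-sided rates of 8.5% at ρ = 0.7 and 7.2% at ρ = 0.9, in agreement with the normal calculation.

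**Step 3: error and power under stated rules.**
- *Fixed sequence, week 10 first:* familywise error at most 5%; week-10 power stays at 87-88%.
- *Both required at 0.05:* the chance that both are falsely significant is 0.05 + 0.05 − 0.083 = 1.7% at ρ = 0.7, and never above 5%. Joint power is about 82% (81.7%) at ρ = 0.7 if week-24 rates equal week-10 rates, or about 76% if week-24 power is 80%. Both week-24 figures are assumptions.
- *Bonferroni, 0.025 each:* error 4.3% at ρ = 0.7; week-10 power 80-81%.

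**Step 4: what the 80% could mean.** Three readings come close:
- both time points required, with equal rates and ρ = 0.7: 81.7%;
- week 10 at alpha 0.025: 80-81%;
- week 24 alone at 0.05 with odds ratio 2.1 and an assumed placebo rate of 15%. The bupropion odds are 2.1 × 0.15/0.85 = 0.371, a rate of 27.0%, and power is 80.3%.

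The text does not separate them.

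**The case against.** The strongest reply is the 80% itself. Power is 88% for week 10 alone and falls to 80% once week 24 and the correlation are brought in. A rule under which either time point suffices would raise power instead. At ρ = 0.7 with equal rates it would be about 87.9 + 87.9 − 81.7 = 94%. The fall fits better with requiring both or with splitting alpha, and either would control the error. This has force: an either-one rule cannot be presented as the authors' intention. But the figure also fits week 24 alone at the full 0.05, and an unexplained power figure does not supply a decision rule.

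Two further points stand. Section 7.2.2 states no alpha for H1, so 0.05 per time point is inferred from section 7.1 and the reproduced 88%. And nothing in the documents ranks week 10 above week 24, so which time point goes first is the investigators' choice.

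A reader might infer that the chance of a false efficacy claim exceeds 5%. The documents do not support that. H1 is directional, and 8.3% includes false findings that bupropion is worse. In bupropion's favour the rate is at most about 4.2%. A reader might also take 8.3% as the plan's error rate; it is an upper end, because the protocol says that ρ is greater than 0.7.

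This is also a phase II trial with two highly correlated readings of one outcome, which bears on severity. But section 1.1 presents it as adequately powered for efficacy and safety, so the error rate of its main claim still matters.

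**Conclusion.** The concern holds as a missing decision rule. H1 has two primary contrasts, and the plan neither orders them, requires both, nor splits alpha. If significance at either may be claimed, two-sided familywise error lies above 5% and up to about 8.3%. In bupropion's favour it lies above 2.5% and up to about 4.2%.

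This rests on three assumptions: each contrast is tested at two-sided 0.05; the protocol's ρ > 0.7 applies to the two test statistics; and either result may count as success, which the plan does not say but does not prevent. If both were meant to be required, there is no inflation, but the 88% is then not the power of the trial's claim. The point covers abstinence only, not the adverse-effect and birth outcomes also listed as primary in section 3.2. Severity: should fix.

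**What to change.** Before unblinding, add one sentence to 7.2.2 that fixes the rule for H1. One option is a fixed sequence: week 10 at two-sided 0.05, then week 24 at two-sided 0.05 only if week 10 is significant. It needs no more participants and keeps week-10 power at about 87-88%. Its cost is that a significant week-24 result alone could not carry the claim.

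Two alternatives also control the error:
- *Hochberg's procedure:* claim both if both p-values are at most 0.05; otherwise claim the smaller if it is at most 0.025. Either time point can then carry the claim. Week-10 power lies between its values at 0.025 (80-81%) and at 0.05 (87-88%).
- *Both required at 0.05:* this costs joint power, as shown in the working.

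Also state in 7.1.1 which test, alpha and week-24 quit rates the 80% refers to, and make it agree with the rule chosen.
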